# **13.2** Analysis Populations and Handling of Dropouts

The Safety Population is defined as all patients who receive the Sonendo GentleWave System procedure.

The Efficacy Evaluable population is defined as all subjects who enroll in the study and who receive 100% of the Sonendo GentleWave Treatment (Treatment Complete Cohort) over the course of no more than two visits. Analysis of efficacy data will be performed using the Efficacy Evaluable population. Efficacy analyses will be based on observed data only; no imputation methods will be used. Dropout subjects will not be replaced.

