## 4.0 STUDY DESIGN

A prospective, non-significant risk device, literature controlled, study evaluating healing rates for the Sonendo GentleWave System in the treatment of 1st and 2nd molars indicated for root canal therapy.

All patients will receive root canal therapy with the Sonendo GentleWave System. All patients will be followed for 24 months post procedure.

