## 7.10 Inability to Complete Treatment

If, for any reason, Sonendo GentleWave treatment cannot be completed over the course of no more than two visits, the subject will be considered as a Treatment Incomplete Subject. Subjects in the Treatment Incomplete Cohort will be documented as such but will not be followed for the study. No additional data will be collected on the Treatment Incomplete Cohort. Reasons for incomplete treatment may include, but are not limited to, periodontal issues, uncontrolled bleeding, root fracture, patient reported pain, etc.

These subjects will be counseled by the PI on any treatment they require. Subjects in the Treatment Incomplete Cohort will be responsible for any standard of care treatment.

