## **13.0 STATISTICAL METHODS**

All required data for this study will be collected on paper or electronic Case Report Forms (CRFs). The Investigator (or designated study staff) will assure primary data collection based on source documented dental chart reviews. Independent monitoring will be performed to ensure that the investigator and his/her study team conducted the clinical investigation in accordance with contract specifications, study protocol, Declaration of Helsinki, and applicable local or national regulations, to ensure adequate protection of the rights and safety of subjects and the quality and integrity of the resulting data.

In general, quantitative variables will be summarized to indicate the population sample size (N), number of patients with available data (n), mean, standard deviation, median, minimum, and maximum values. Qualitative variables will be summarized by the population size (N), number of patients with available data (n), number of patients in each category, and the percentage of patients in each category. Analyses will be based on the Safety Population defined as all patients who receive the Sonendo GentleWave System procedure. Details of analysis methods will be described in the statistical analysis plan.

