## 13.1 Sample Size

All patients will receive root canal therapy with the Sonendo GentleWave System and will be subsequently followed for 24 months post procedure. A sample size of 108 subjects, assuming a 20% lost to follow-up or Treatment Incomplete Cohort rate, will result in approximately 86 subjects who would be evaluable for the primary efficacy endpoint. A sample size of 86 evauable subjects provides approximately 90% power to detect a difference between a 85% response rate for subjects using the Sonendo GentleWave System against a null hypothesis of a 70% response rate based on data presented in literature for traditional root canal therapy, using a two-sided binomial test at the 5% level of significance.

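### The primary healing rate is conditional on completing the GentleWave Treatment within two visits, and no efficacy analysis shows the rate among all enrolled subjects

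*Combined protocol and SAP*

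**What the plan says.** **Enrolment.** Section 7.6 counts a patient as enrolled once all criteria are met and placement of the LuxaBite material or Tooth Cap begins. Section 7.7 defines this as the start of the device treatment. A Treatment Incomplete subject is therefore enrolled and in device treatment, not a screen failure.

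**Removal.** Section 7.10 classes a subject as Treatment Incomplete if the treatment cannot be finished in two visits. Its examples are periodontal issues, uncontrolled bleeding, root fracture and patient-reported pain. These subjects are documented as incomplete but not followed: "No additional data will be collected on the Treatment Incomplete Cohort".

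**Primary rate.** Sections 3.1 and 13.4 define the primary rate in the Treatment Complete cohort. Section 13.2 agrees: "Analysis of efficacy data will be performed using the Efficacy Evaluable population".

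**Conflicting statements on follow-up.** Section 4.0 says: "All patients will be followed for 24 months post procedure". The synopsis design row and 13.1 say the same. The synopsis cohort row and 7.10 limit follow-up to Treatment Complete subjects.

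**Conflicting statements on population.** Section 13.0 says: "Analyses will be based on the Safety Population defined as all patients who receive the Sonendo GentleWave System procedure". Section 13.2 uses the Efficacy Evaluable population for efficacy.

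**Sample size.** Section 13.1 plans 108 subjects with a single 20% allowance that covers loss to follow-up and Treatment Incomplete together, and says this "will result in approximately 86 subjects who would be evaluable for the primary efficacy endpoint".

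**The concern.** Completion is known only after enrolment, and some of the listed reasons for non-completion are events that arise during treatment. Restricting the rate to completers therefore selects on something that happens after the device is first applied. If incomplete cases do worse than completed ones, the reported rate is higher than the rate among all subjects in whom the device was started.

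The trial has one arm and a fixed 70% benchmark, so no concurrent control group loses subjects in the same way. The plan expects some incomplete cases, because they share the 20% allowance, but it gives no separate figure for them and no analysis that would show their effect.

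The contradictions add a practical problem. A site cannot tell from 4.0 and 7.10 together whether a Treatment Incomplete subject is to be recalled, and 13.0 and 13.2 name different populations.

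**Working it through.** **Inputs, all from 13.1.** Null rate 70% ("null hypothesis of a 70% response rate based on data presented in literature for traditional root canal therapy"), alternative 85%, 86 evaluable subjects, and the method "using a two-sided binomial test at the 5% level of significance". Total 108 with a 20% allowance. The split of that allowance is not given.

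**1. The plan's own figures.**
- Inflation: 86 / 0.80 = 107.5, rounded up to 108. The allowance is 108 − 86 = 22 subjects.
- Exact test: the smallest number of successes x with P(X ≥ x | n = 86, p = 0.70) ≤ 0.025 is 69 (80.2%), where the tail is 0.0223.
- Power: P(X ≥ 69 | n = 86, p = 0.85) = 0.914. The stated "approximately 90% power to detect a difference between a 85% response rate" is reproduced.

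**2. Worst-case rate including incomplete subjects.** Let x be the successes among 86 completers and k the number of Treatment Incomplete subjects, all counted as not healed. The rate is x / (86 + k), with an exact (Clopper-Pearson) 95% interval. At x = 73, the result nearest the planned 85%:

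| k | x / (86 + k) | Rate | Exact 95% CI | Excludes 70%? |
|---|---|---|---|---|
| 0 | 73/86 | 84.9% | 75.5 to 91.7 | yes |
| 4 | 73/90 | 81.1% | 71.5 to 88.6 | yes |
| 5 | 73/91 | 80.2% | 70.6 to 87.8 | yes |
| 6 | 73/92 | 79.3% | 69.6 to 87.1 | no |
| 11 | 73/97 | 75.3% | 65.5 to 83.5 | no |

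The values of k are assumptions. The documents allow anything from 0 to about 22.

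**3. How the tipping number moves with x.** The smallest k at which the interval includes 70%:

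| Successes among 86 | 69 | 70 | 71 | 73 | 74 |
|---|---|---|---|---|---|
| Tipping k | 1 | 2 | 3 | 6 | 7 |

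For example, 74/92 is 80.4% (70.9 to 88.0) and still excludes 70%.

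**4. The reverse question.** Suppose the true success rate among all enrolled subjects is exactly 70% and incomplete cases never succeed. With an incomplete rate q, the completers' rate is 0.70 / (1 − q).
- q = 5%: 0.70 / 0.95 = 73.7%. The chance of 69 or more successes among 86 completers is 10.2%.
- q = 10%: 0.70 / 0.90 = 77.8%. The chance is 34.6%.

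The nominal upper tail is 2.2%. This comparison matters only if 70% is the right benchmark for all enrolled subjects, which the documents do not establish.

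**The case against.** **The restriction is open and planned for.** The synopsis, 3.1, 13.2 and 13.4 all state it, and 13.1 inflates the sample for it. This stands. The primary analysis is not invalid, and the power calculation is sound.

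**The direction against the literature is unknown.** A reader might infer that the rate is biased upward against the 70% control. That depends on whether the literature rates counted uncompleted treatments. Section 2.3 gives no denominator rule, and the Healing Literature Report is not in the text supplied. If the literature rates also cover completed treatments only, the Treatment Complete cohort is the like-for-like comparison, and counting incomplete cases as failures would understate the device. This stands. What can be said is that the rate overstates success among all enrolled subjects if incomplete cases do worse.

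**Completion is not success.** A reader might take the rate to be conditional on the device working. Section 7.13 defines the end of treatment by the console display reaching 100%, which says nothing about healing. Some reasons for stopping, such as periodontal issues, need not be device failures. Scoring every incomplete case as not healed is therefore a worst case.

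**These subjects are not invisible.** Section 13.6 summarises the device-related safety events in the Safety Population, and 7.10 stops only additional data. The gap concerns efficacy. Section 13.0 also defers details of method to a statistical analysis plan, so the absence of a sensitivity analysis is claimed only for the supplied text.

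**Six may be too many to expect.** The synopsis lists 18 subjects for loss to follow-up alone. Set against the 22 in 13.1, that would leave 4, and 73/90 still excludes 70%. The inference is rough, because the synopsis components (86 + 18 = 104) do not match 108. It does show that six cannot be presented as the expected number.

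**Conclusion.** The point holds as a limitation of the planned efficacy reporting. The primary rate describes subjects who completed the device treatment in at most two visits, and nothing in the supplied text gives a corresponding rate for all enrolled subjects. The statements on follow-up and on analysis population contradict each other.

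The size cannot be fixed from the documents. At the planned success rate, five incomplete subjects scored as failures leave the interval above 70% and six do not. Nearer the critical value of 69/86 a single subject is enough, and above 73/86 more than six are needed. These figures assume 86 completers with an outcome, the exact interval, and failure for every incomplete subject. A reader might conclude that six incomplete subjects would overturn the trial, but that holds only at exactly 73/86 under worst-case scoring.

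**What to change.** 1. Keep the Efficacy Evaluable population as primary.
2. Add to 13.4 a prespecified sensitivity analysis in all enrolled non-roll-in subjects, with Treatment Incomplete counted as not healed, labelled as worst case and reported with the exact 95% interval. Treat Treatment Complete subjects exactly as in the primary analysis, so that the two rates differ only by the incomplete cases.
3. Report the number of Treatment Incomplete subjects and the reason for each.
4. Reconcile the follow-up statements in the synopsis design row, 4.0 and 13.1 with the synopsis cohort row and 7.10, and the population in 13.0 with that in 13.2.

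**Cost.** One additional analysis and some wording. It needs no extra visits or subjects, since 7.10 already has incomplete cases documented. The downside is a second rate that cannot be more favourable than the first. If incomplete cases are rare, the two rates will nearly agree and the primary result is strengthened.

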## 2.2.4 Perforation

Root perforations are shown to be one of the eminent causes of endodontic failures. They are artificial openings in root walls created by boring, piercing, or filing that result in a communication between the pulp space and periodontal tissues. These openings may cause secondary periodontal involvement and eventual loss of the tooth. latrogenic perforations are often due to insufficient attention to the details of internal anatomy and a failure to consider anatomic variations. They may also be due to lack of information on the canal anatomy and morphology, as the dental radiographs only provide a buccolingual view of the tooth. Accidental root perforations, which may have serious implications, occur in approximately 2–12% of endodontically treated teeth. Bacterial infection emanating either from the root canal or the periodontal tissues, or both, prevents healing and promotes inflammatory sequels where the supporting tissues have been exposed. This bacterial exposure may be followed by painful conditions, abscesses, and fistulae, including bone resorption processes. Once an infectious process has established itself at the perforation site, prognosis for treatment is precarious and the complication may prompt extraction of the affected tooth.

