#### **3.1** Primary Effectiveness Endpoints

Subject teeth in the Treatment Complete cohort that are healed or are healing at the twentyfour month Follow-up Visit.

Healed is defined by absence of a radiographic indication of apical periodontitis (PAI <3) and absence of clinical signs and symptoms.

Healing is defined by a reduction of radiolucency (if radiolucency is present at Baseline) and/or reduction of clinical signs and symptoms (if clinical signs and symptoms are present at Baseline)

Secondary analysis will be performed after all Treatment Complete subjects have completed the 12 month Follow-up Visit.

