#### **3.3 Secondary Endpoints**

The following outcomes will be assessed:

- 1. McGill Short Form Pain Questionnaire
- 2. Gracely Descriptor Differential Scale (DDS) 59
- 3. Patient Satisfaction Survey
- 4. AAE Case Difficulty Assessment
- 5. Soft Tissue Lesions
- 6. Swelling
- 7. Root Canal Therapy Retreatment
- 8. Treatment Time
- 9. Procedure Time
- 10. Periapical Index (PAI) analyzed utilizing radiographic analysis by independent reviewer
- 11. Cone Beam Computed Tomography (CBCT) Sub-Set Evaluation
- 12. Additional Radiographic Analysis may be completed

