- Acute Apical Abscess: An inflammatory reaction to pulpal infection and necrosis characterized by rapid onset, spontaneous pain, tenderness of the tooth to pressure, pus formation, and swelling of associated tissues.
- Chronic Apical Abscess: An inflammatory reaction to pulpal infection and necrosis characterized by gradual onset, little or no discomfort, and the intermittent discharge of pus through an associated sinus tract.
- Condensing Osteitis: Diffuse radiopaque lesion representing a localized bony reaction to a low-grade inflammatory stimulus, usually seen at apex of tooth
- 8. Adverse Events (see Section 10.0 Adverse Event).

After assessments are completed, the patient may be prescribed medication(s) for pain management according to standard of care procedures. If analgesic medications need to be provided to the patient in order to complete one or more of the assessments, the assessments that require a pain response (i.e. cold test, percussion and palpation) should be completed prior to providing this medication.

All redacted source documentation with PI signature should be provided to the Sponsor for filing after each study visit. If changes are made to the source documents after PI signature, the updated source documents should be provided to the Sponsor for filing.

In addition, the clinical site designee will report all significant findings at Follow-Up Visits to the Sponsor either via email or by sending redacted source documentation.

Subjects should be evaluated to determine if the subject tooth remains functional. If the subject tooth is or still requires healing, the subject should be evaluated closely. If the subject has clinical symptoms or signs after the twelve month follow-up, the PI should follow standard endodontic care, as applicable. All such care should be documented accordingly for the study.

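### No rule says how a subject tooth extracted before month 24 counts in the primary endpoint, and no written route guarantees that it counts as a failure

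*Combined protocol and SAP*

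**What the plan says.** Section 3.1 sets the primary endpoint as "Subject teeth in the Treatment Complete cohort that are healed or are healing at the" 24-month visit. It defines two favourable states. The first: "Healed is defined by absence of a radiographic indication of apical periodontitis (PAI <3) and absence of clinical signs and symptoms". The second: "Healing is defined by a reduction of radiolucency (if radiolucency is present at Baseline) and/or reduction of clinical signs and symptoms". Failure is not defined, and tooth loss is not mentioned.

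Four provisions bear on a tooth that is no longer there at month 24:

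- Section 13.2: "Efficacy analyses will be based on observed data only; no imputation methods will be used".
- Section 13.7 prescribes LOCF for missing data and, in the next sentence, a complete-case analysis.
- Section 9.7 allows subjects terminated for treatment-related reasons to be left out of the final analysis.
- Section 7.17.2 has the investigator check whether the tooth is still functional, without linking this to the endpoint. It adds: "If the subject has clinical symptoms or signs after the twelve month follow-up, the PI should follow standard endodontic care, as applicable".

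Among the secondary endpoints, 3.3 lists "Root Canal Therapy Retreatment" but not extraction. Section 13.4 promises a proportion with an exact 95% confidence interval, and 13.1 sets that proportion against a 70% literature rate. Section 13.0 leaves analysis details to a statistical analysis plan; no separate plan text is in the document supplied.

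**The concern.** An extracted tooth has no 24-month radiograph, PAI score, percussion result or palpation result. To the analysis rules it looks like a missing value. When the tooth was lost for an endodontic reason, the outcome is known and unfavourable.

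Sending such a tooth through the missing-data rules can remove a failure from the denominator or preserve an earlier favourable rating. The trial has a single arm and a fixed comparator, so no concurrent control group is subject to the same handling.

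The event is plausible. Root fracture is a component of the primary safety endpoint (3.2), abscess and root fracture are among the anticipated risks (10.8, 10.10), and 7.17.2 foresees teeth that still have signs or symptoms after month 12, up to a year before the primary reading. What is at stake is who counts as a success on the primary endpoint.

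**Working it through.** **Inputs.** From 13.1: 86 evaluable teeth, 108 enrolled, 20% attrition, null rate 70%, alternative 85%, two-sided 5% binomial test, about 90% power. From 13.4: exact 95% confidence interval. Assumed, because the documents give no figure: the number of extractions k, the extraction probability e, and a success criterion (exact lower limit above 70%), which 13.4 does not state.

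**The plan's own figures.** With 2.5% per tail, P(X ≥ 68 | n = 86, p = 0.70) = 0.0396 is too large and P(X ≥ 69) = 0.0223 is allowed, so the cut-off is 69/86. Power is P(X ≥ 69 | p = 0.85) = 0.914, against about 90% stated. 86 / (1 − 0.20) = 107.5, rounded up to 108. Both reproduce.

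**Direction.** Let s be the successes among teeth still present, k the extractions and n the total.

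- Extraction as failure: s/n.
- Observed data, complete case, or exclusion under 9.7: s/(n − k), which is higher whenever k ≥ 1 and s > 0.
- LOCF: (s + j)/n, where j (0 ≤ j ≤ k) is the number of extracted teeth last rated healed or healing. This equals s/n when all were last rated unhealed and is higher otherwise.

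No route falls below s/n, and none ensures s/n.

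**Size on assumed counts** (exact 95% lower limit in brackets):

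| s | k | Failure, s/86 | Dropped, s/(86 − k) | LOCF, j = k |
|---|---|---|---|---|
| 68 | 2 | 79.1% (69.0%) | 68/84 = 81.0% (70.9%) | 70/86 = 81.4% (71.6%) |
| 66 | 4 | 76.7% (66.4%) | 66/82 = 80.5% (70.3%) | 70/86 = 81.4% (71.6%) |
| 73 | 2 | 84.9% (75.5%) | 73/84 = 86.9% (77.8%) | 75/86 = 87.2% (78.3%) |
| 73 | 4 | 84.9% (75.5%) | 73/82 = 89.0% (80.2%) | 77/86 = 89.5% (81.1%) |

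If the extracted teeth are dropped, the conclusion changes only at s = 68 for k = 2, and only at s = 66, 67 or 68 for k = 4. Near 85% it does not change.

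**Error rate.** Suppose the true success rate, with extraction as failure, is exactly 70%. The upper-tail error is then 2.2%. If extractions are dropped, the rate among retained teeth is 0.70/(1 − e): 71.4% at e = 2% and 73.7% at e = 5%. Averaging over the number extracted, Binomial(86, e), with the exact cut-off for each remaining n, the error becomes 3.3% and 8.3%. In the LOCF extreme, where every extracted tooth was last rated a success, the rate is 0.70 + e and the error is 5.3% and 16.0%.

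**The case against.** Several points on the other side stand.

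- A reader might infer that no version of the plan yields a failure, or that losing a tooth always raises the success rate. The LOCF sentence of 13.7 contradicts this: a tooth last rated neither healed nor healing is carried forward as a non-success and stays in the denominator.
- A reader might infer that an extracted tooth could be scored as healing because its baseline pain has gone, through the limb "and/or reduction of clinical signs and symptoms (if clinical signs and symptoms are present at Baseline". This reading is strained. Section 3.1 speaks of subject teeth that are healed or healing, and 7.17.2 expects a periapical radiograph of the tooth. An absent tooth is hardly one that is healing.
- A reader might infer that the bias always favours the device. That is not shown for the comparison with 70%. Section 2.3 says endpoints vary across the literature, and nothing supplied says how those studies counted extractions. If they excluded them, counting them as failures here alone would work against the device.
- Foreseeability is thinly documented. The remark that "the complication may prompt extraction of the affected tooth" in 2.2.4 is background on infected perforations in conventional therapy, and 5.4 excludes perforated teeth before enrolment. Section 7.17.2 refers to standard care without naming extraction.
- The illustration lies at the boundary, on assumed counts and an inferred criterion.

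It could also be said that settling 13.2 against 13.7 would resolve this. It would not: complete case drops the tooth, and LOCF may score it a success. Only an endpoint rule closes the gap, so the conflict between those sections is a separate matter.

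**Conclusion.** The point holds in this form: the primary endpoint has no classification for a subject tooth extracted before month 24, and no written route guarantees that it counts as a failure. Relative to counting it as a failure, observed-data, complete-case and 9.7 handling give a higher rate, and LOCF gives an equal or higher one. That ordering is arithmetic and needs no assumed extraction rate.

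The size does rest on assumptions. Two dropped extractions move 68/86 across the 70% line, but no other success count out of 86. A 2% to 5% extraction rate takes the upper-tail error from 2.2% to between 3.3% and 8.3% if extractions are dropped. Results near 85% would keep their conclusion. The direction is established within this trial only, not against the literature rate.

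**What to change.** - State in 3.1, 13.2 and 13.4 that a subject tooth extracted for any reason before the 24-month visit counts as not healed, stays in the denominator, and is not subject to the missing-data rules. Covering any reason avoids leaving periodontal or restorative losses without a primary rule.
- Report the number, dates and reasons of extractions beside the primary rate.
- Add a sensitivity analysis that treats as missing any extraction clearly unrelated to the treated tooth's endodontic outcome, with the reason recorded on the CRF and classified before analysis.
- Record extraction date and reason on the existing follow-up CRF and in the 7.19 contact.
- State how the studies behind the 70% rate counted extractions, or that this is unknown.

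The cost is wording and the added CRF fields, with no extra visits. The reported rate may fall slightly. If the 85% in 13.1 was meant for retained teeth only, power with 86 teeth falls from 91.4% to 82.0% at a 2% extraction rate (0.85 × 0.98 = 0.833) and to 61.2% at 5% (0.85 × 0.95 = 0.8075). Section 13.1 should therefore say which meaning applies.
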